7.3 Body Weight and Vital Signs

Descriptive statistics will be provided by treatment group for body weight and vital signs as follows:

- Baseline
- Postbaseline maximum
- Postbaseline minimum
- Change and percentage change from baseline to postbaseline maximum
- Change and percentage change from baseline to postbaseline minimum

A baseline value is defined as the last available value collected on or prior to the first dose of study drug.

A by-subject listing of body weight and vital signs will be provided by subject ID and time point in chronological order.

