9.4 Statistical Analyses

9.4.1 Safety Analyses

Safety analyses will be performed separately within both phases of the study and for all patients combined. Data from all patients that receive any portion of at least one dose of FPA150 as monotherapy or one dose of FPA150 in combination with pembrolizumab will be included in the safety analyses. AEs, clinical laboratory information, vital signs, ECOG performance status, weight, ECGs, and concomitant medications/procedures will be tabulated and summarized. In addition, the incidence of DLTs in Phase 1a will be summarized.

Subject incidence of AEs will be summarized overall and with separate summaries for serious AEs, AEs leading to discontinuation, AEs leading to death, and NCI CTCAE Grade 3 or higher AEs. The patients' worst grade for each preferred term will be used for the summary of AEs by CTCAE grade. Treatment-related AEs and SAEs will also be summarized similarly.

Weight and vital signs will be summarized descriptively (N, mean, SD, median, minimum, and maximum). ECOG performance status will be summarized categorically and descriptively.

Shift tables displaying patient counts and percentages classified by baseline grade and maximum grade on treatment will be provided for laboratory data by cohort and overall as appropriate.

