- e. Vital signs include pulse, respiratory rate, blood pressure, and temperature in a resting position. Measure vital signs prior to dosing and after completion of each IV infusion at the following time points: 5 minutes (± 3 min), 15 minutes (± 3 min), 30 minutes (± 3 min), and 1 hour post-dose (± 15 min). In addition, measure vital signs at 2, 3 and 4 hours post-dose (± 15 min) in patients that are being monitored for up to 4 hours post-dose (ie, after 1st infusion of FPA150 or after the end of infusion at each inpatient dose escalation).
- f. The exact time of the ECG should be recorded. The results will include heart rate, PR interval, QRS interval, QT interval, and QTc interval. Additional ECGs should be obtained at any time, if serum CK or cardiac troponin is elevated; if abnormal (excluding sinus tachycardia), ECGs should be obtained (if clinically indicated), until the abnormality is resolved or clinically stable. Additional ECGs may be obtained at any time, if clinically indicated. ECGs for each patient should be obtained from the same machine whenever possible. ECGs should be performed before the PK blood draw on days where both are done. To minimize variability, it is important that patients be in a resting position for at least 5 minutes prior to each ECG evaluation. Body position should be consistently maintained for each ECG evaluation to prevent changes in heart rate. Environmental distractions (eg, television, radio, conversation) should be avoided during the pre-ECG resting period and during ECG recording. Any clinically significant changes in ECGs that occur during the study should be reported as an AE in the eCRF.
- g. ECOG status is to be assessed at Screening, within 72 hours prior to dosing on Day 1 of each cycle, and at EOT.
- h. A biopsy will be collected from the primary tumor or metastatic tumor site in patients enrolled in Phase 1a Monotherapy Dose Exploration, and a subset of patients (15 patients per 30-patient dose cohort) in Phase 1b Monotherapy Dose Expansion and Phase 1b Combination Dose Expansion cohorts; this will be done at screening and prior to the Cycle 3, Day 1 dose, from the same lesion where feasible. Refer to Section 8.4 for details regarding analyses of tumor tissue (fresh or archival).

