- n. Samples will be collected for PK, ADA, and pharmacodynamic analyses. All ADA and all PK samples should be collected prior to dosing. Not all visits will require collection of all 3 samples (PK, ADA, and Pharmacodynamic); refer to [Appendix 2](#) for the collection schedule; refer to [Appendix 3](#) for a list of the pharmacodynamic analyses. FPA150 samples for PK, ADA, and pharmacodynamic analyses will be assessed at a central laboratory. For cohorts of FPA150 in combination with pembrolizumab samples for PK will be collected and held at a central laboratory. In addition to the visits noted in Schedule of Assessments, PK and PD samples will be drawn on Day 4 and PK samples will be drawn on Day 15 of Cycle 1 for all cohorts.
- o. FPA150 will be administered as a 60-minute (\pm 5 minutes) IV infusion Q3W in 21-day cycles until progressive disease or unacceptable toxicity. For FPA150 in combination with pembrolizumab cohorts, pembrolizumab will be administered after completion of the FPA150 IV infusion. Pembrolizumab will be administered at a dose of 200 mg by IV infusion over 30 minutes (\pm 5 minutes) starting on C1D1 and repeated Q3W on Day 1 of each 21-day cycle after all procedures and assessments have been completed. Pembrolizumab should not be co-administered with FPA150 through the same IV line. All patients must be monitored for at least 4 hours after the end of the first infusion of FPA150 and/or pembrolizumab. Patients may continue receiving FPA150 monotherapy or both drugs in combination according to their study specified cohort/dose until Investigator-assessed disease progression or the patient meets any of the other protocol-specified withdrawal criteria (refer to Section 7)
- p. Only applicable for patients enrolled in Phase 1b cohorts, or the patient completes approximately 2 years of pembrolizumab. If one of the two drugs have to be discontinued, patients may continue to receive the other drug alone (based on Investigator discretion). Patients should be contacted every 12 (\pm 2) weeks for survival status for up to 2 years. Patients should have tumor scans every 12 (\pm 2) weeks, if tumor progression was not previously determined and/or use of alternative anti-cancer therapy has not been initiated. Any new anti-cancer therapy should be documented.
- q. To minimize lab draws for patients, any labs obtained during screening that fall within the window of 3 days prior to C1D1 can be used for dosing purposes.

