3 GENERAL CONSIDERATIONS

All statistical tabulations and analyses will be done using SAS[®], Version 9.3 or higher.

Unless otherwise noted, continuous variables will be summarized using the number of subjects (n), mean, standard error (SE) or standard deviation (StD), median, minimum, and maximum; categorical variables will be summarized using the number and percentage of subjects in each category.

By-subject listings will be presented for all subjects in the Safety Analysis Set and sorted by phase, treatment group, subject ID number, visit date, and time (if applicable). Data collected on log forms, such as AEs, will be presented in chronological order within the subject. The treatment group to which subjects were enrolled will be used in the listings. Age, sex at birth, race, and ethnicity will be included in the listings, as space permits.

The summaries of the efficacy data will be presented by treatment group.

Unless stated otherwise, summaries will be provided separately for the following 3 groups of subjects:

- Phase 1a (Dose Escalation + Exploration)
- Phase 1b (Monotherapy)
- Phase 1a (Combination Safety Lead-in) and Phase 1b (Combination)

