3.7.2 Analysis Visit Windows

No analysis visit window will be assigned in the analysis as no summary by visit is planned.

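### The vital-sign tables in SAP 7.3 report change only to each patient's maximum and minimum, which is non-zero with no drug effect, grows with exposure, and makes no use of the scheduled post-infusion times

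*SAP*

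**What the plan says.** SAP 7.3 lists, by treatment group, the baseline value, the post-baseline maximum, the post-baseline minimum, and the change to each extreme, for example "Change and percentage change from baseline to postbaseline maximum". Baseline is one value, the last available on or before the first dose. Under SAP section 3, "continuous variables will be summarized using the number of subjects (n), mean, standard error (SE) or standard deviation (StD), median, minimum, and maximum". SAP 7.3 also promises a listing: "A by-subject listing of body weight and vital signs will be provided by subject ID and time point in chronological order". No change at a scheduled time and no count of patients crossing a threshold is specified. SAP 3.7.2 states: "No analysis visit window will be assigned in the analysis as no summary by visit is planned".

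The protocol collects far more structure than this. Appendix 1, footnote e: "Measure vital signs prior to dosing and after completion of each IV infusion at the following time points", namely 5, 15 and 30 minutes and 1 hour. For patients monitored for 4 hours, as all are after the first FPA150 infusion: "In addition, measure vital signs at 2, 3 and 4 hours post-dose". In the combination cohorts there are two infusions per cycle, because "pembrolizumab will be administered after completion of the FPA150 IV infusion" (footnote o).

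SAP 3.7.3 treats only measurements after the first dose date as post-baseline.

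Protocol 9.4.1 asks only for a descriptive summary: "Weight and vital signs will be summarized descriptively (N, mean, SD, median, minimum, and maximum").

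**The concern.** A maximum taken over many noisy readings, minus one noisy reading, has a positive expectation whatever the drug does. The minimum behaves the same way in the other direction. The size depends on how many readings the patient contributed, and here that number varies by design and by outcome. A combination cycle can yield twice as many post-infusion readings as a monotherapy cycle, and patients who stay on treatment longer contribute more. FPA150 monotherapy has no cap on doses, and there is no control arm to show what the table looks like without an effect.

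The schedule in footnote e is suited to picking up changes around the infusion, yet no planned table uses it. Blood pressure is of some interest here: protocol 2.2.5.5 reports one Grade 3 treatment-related AE among 24 patients, and it was hypertension.

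**Working it through.** The documents give no figure for this summary, so there is nothing of the plan's own to reproduce. The check asks what the SAP 7.3 statistic is expected to show when nothing has changed.

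**Inputs**
- Readings per patient, from Protocol Appendix 1 (Table 12 and footnote e). Counting only days after the first dose date (SAP 3.7.3 read literally): Day 8 gives 1; each later cycle gives 1 pre-dose plus 4 post-infusion = 5 for monotherapy, or 1 + 8 = 9 for combination (an upper figure); the two end-of-treatment visits give 2.
- Number of doses: median 3, range 1 to 11 (Protocol 2.2.5.3).
- Within-patient SD: not in the documents. Assumed 10 mmHg for systolic pressure.
- Correlation of readings within a visit: not in the documents. Taken as 0, 0.5 and 0.8.

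**Number of readings**, m = 1 + (doses − 1) × k + 2, with k = 5 or 9:
- 3 doses: 1 + 2×5 + 2 = 13 (monotherapy); 1 + 2×9 + 2 = 21 (combination).
- 11 doses: 1 + 10×5 + 2 = 53; 1 + 10×9 + 2 = 93.

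**Expected change with no effect.** For independent normal readings it is SD × E[max of m], where E[max of m] = ∫ x·m·φ(x)·Φ(x)^(m−1) dx. Correlated readings were simulated. Change to maximum in mmHg; the change to minimum is the mirror image:

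| | correlation 0 | 0.5 | 0.8 |
|---|---|---|---|
| Monotherapy, 3 doses | 16.8 | 15.2 | 13.8 |
| Combination, 3 doses | 18.9 | 16.7 | 14.7 |
| Monotherapy, 11 doses | 22.6 | 21.8 | 20.4 |
| Combination, 11 doses | 24.8 | 23.6 | 21.4 |

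These values are proportional to the SD. At SD 5 the 3-dose range is 13.8×0.5 to 18.9×0.5, about 7 to 9 mmHg; at SD 12 it is 13.8×1.2 to 18.9×1.2, about 17 to 23 mmHg.

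**If the Day 1 post-infusion readings are counted** (4 + 3 more for monotherapy, so 20 readings at 3 doses and 60 at 11), the monotherapy values are 15.6 to 18.7 and 20.7 to 23.2 mmHg over the same correlations. The conclusion does not turn on that choice.

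**What the statistic can and cannot show** (SD 10, correlation 0.5):
- Unequal exposure: with Day 1 counted and no effect, 2 cycles give 15.6 and 8 cycles give 21.0, a difference of 5.4 mmHg from exposure alone.
- Brief effect: with Day 1 counted, 3 cycles, a true +15 mmHg at one reading after the first infusion moves the mean change to maximum from 17.2 to 20.2. With Day 1 excluded, that reading would not enter at all.
- Sustained effect: with 13 readings, a true +10 mmHg shift gives about +25.3/−5.2, against +15.2/−15.3 with no effect. The midpoint, (25.3 − 5.2)/2 = 10.05, recovers the shift.

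**Comparison.** A mean change at a fixed time point has expectation 0 with no effect and equals the shift when there is one, whatever the number of cycles.

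**Weight**, also covered by SAP 7.3, has far fewer readings (2, 4 and 12 at 1, 3 and 11 cycles). The corresponding inflation is 0.56, 1.03 and 1.63 SD.

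**First-infusion readings.** SAP 7.3 takes baseline at or before the first dose, so these readings are not baseline; SAP 3.7.3 takes post-baseline as after the first dose date, so they are not post-baseline either. Taken literally, the readings from 5 minutes to 4 hours after the first infusion appear only in the listing.

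**The case against.** The case for leaving the plan alone has real content.

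- A reader might infer that vital signs are summarized only as a mean change. The documents do not support that: baseline, both extremes, medians, SDs and ranges are planned as well, and the chronological listing keeps the timing.
- A reader might also infer that the tables cannot show a real effect. That is too strong. A sustained shift breaks the mirror symmetry of the two changes and can be read from them.
- Clinically significant events have another route. Protocol 6.4.6 names hypotension and hypertension with headache among infusion-reaction symptoms, SAP 4.2 summarizes infusion interruptions with reasons, and SAP 7.1.6 tabulates AEs by severity. The Grade 3 hypertension itself came through AE reporting.
- Vital signs are not a named endpoint in either phase, SAP section 7 plans no formal safety comparisons, and combination patients are summarized apart from monotherapy. The extra readings per combination visit add only 0.9 to 2.1 mmHg at 3 doses. With a between-patient SD of change of about 11.5 and 30 patients per group, the standard error of a difference is √(2 × 11.5²/30) ≈ 3 mmHg, so that gap is below sampling error.
- Protocol 9.4.1 requires only a descriptive summary, and this is one. Full tables by cycle would be sparse, since accelerated-titration levels may hold a single patient.

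All of this stands, and it limits the point to the change tables. It does not answer that point: a listing is not a summary, the change tables offer no null value to be read against, and differences in time on treatment matter more than the second infusion.

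**Conclusion.** The concern holds in a limited form. The vital-sign change tables are displaced from zero with no drug effect and depend on exposure. They are poorly suited to brief infusion-related or modest effects and to informal comparison of groups with different time on treatment. The displacement is about 14 to 19 mmHg at 3 doses and 20 to 25 mmHg at 11, on an assumed SD of 10 mmHg and within-visit correlation between 0 and 0.8. Growth with the number of readings follows for any positive SD unless readings are perfectly correlated. No endpoint, sample size or error rate is affected. This is an inexpensive improvement to a descriptive safety output.

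**What to change.** Keep the maximum and minimum summaries, labelled as supplementary, and add:

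- change from the same-visit pre-dose value at the nominal post-infusion times in Protocol Appendix 1, footnote e, at least for Cycle 1, by drug infused;
- change from baseline in the pre-dose value at each Day 1 visit, for cycles with enough patients, with n shown.

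Amend SAP 3.7.2 so that these summaries are planned, and SAP 3.7.3 so that readings taken after the start of the first infusion on Day 1 count as post-baseline.

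The data and nominal times already exist, so the cost is one or two tables and a few lines of SAP text. The downside is sparse cells in small dose groups and late cycles, where the means also describe only patients still on treatment. That is why the first table can stop at Cycle 1 and the second should show n.

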7.4 Electrocardiograms

Subjects with abnormal ECG findings will be listed.

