3.2 Phase 1b Objectives and Endpoints

The objectives and endpoints for Phase 1b of the study are summarized in Table 2. Additional information regarding study assessments and procedures is provided in Section 8; statistical analysis information is provided in Section 9.

Table 2: Objectives and Endpoints: Phase 1b

OBJECTIVES	ENDPOINTS
PRIMARY - SAFETY	
FPA150 Monotherapy 
 To evaluate the safety and tolerability of FPA150 as monotherapy in patients with B7-H4+ advanced solid tumors treated at the MTD and/or RD 	FPA150 Monotherapy 
 The incidence of AEs, clinical laboratory abnormalities, and ECG abnormalities

OBJECTIVES	ENDPOINTS

FPA150 Combined with Pembrolizumab
 
 To evaluate the safety and tolerability of FPA150 in combination with pembrolizumab in selected patients with B7-H4+ ovarian cancer treated at the MTD and/or RD 	
FPA150 Combined with Pembrolizumab
 
 The incidence of AEs, clinical laboratory abnormalities, and ECG abnormalities in patients treated with FPA150 in combination with pembrolizumab
SECONDARY - EFFICACY	

FPA150 Monotherapy
 
 To evaluate the clinical benefit of FPA150 as monotherapy in patients with B7-H4+ advanced solid tumors treated at the MTD and/or RD 	
FPA150 Monotherapy
 
 ORR, defined as the total number of patients with confirmed responses of either CR or PR per RECIST v1.1 divided by the total number of patients who are evaluable for a response DOR, defined as the time from onset of response (CR or PR) that is subsequently confirmed to the first observation of progressive disease or death due to any cause PFS, defined as the time from the patient's first dose to the first observation of progressive disease or death due to any cause)

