8.3.3 Electrocardiograms

Twelve-lead ECGs will be performed in accordance with the Schedule of Assessments ([Appendix 1](#)). To minimize variability, it is important that patients are in a resting position for at least 5 minutes prior to each ECG evaluation. Body position should be consistently maintained for each ECG to prevent changes in heart rate. ECGs for each patient should be obtained from the same machine whenever possible. The ECGs should be reviewed promptly by a qualified physician and any clinically important finding should be recorded on the appropriate CRF. The Investigator is responsible for providing the interpretation of all ECGs. The results will include heart rate, PR interval, QRS interval, QT interval, and QTc interval.

ECGs should be performed before the PK blood draw on days where both are done. Additional ECGs should be obtained at any time if serum creatine kinase (CK) or cardiac troponin is elevated, or if ECG is abnormal (excluding sinus tachycardia; ECGs should be obtained [if clinically indicated] until the abnormality is resolved or clinically stable). Additional ECGs may be obtained at any time, if clinically indicated (eg, in case of elevated creatinine kinase [CK] or troponin).

Any clinically significant changes in ECGs that occur during the study should be reported as an AE in the eCRF.

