7.1.6 Summary of Adverse Events and Deaths

The number and percentage of subjects who experienced at least 1 TEAE will be provided and summarized by SOC, PT, and treatment group. For other AEs described below, summaries will be provided by SOC, PT, maximum severity, and treatment group

- TEAE
- TE SAE
- Summary of TEAE of Grade 3-5
- TEAE related to FPA150
- TEAE leading to FPA150 treatment discontinuation
- TEAE leading to death
- TEAE of dose limiting toxicity

A brief, high-level summary of AEs described above will be provided by treatment group and by the number and percentage of subjects who experienced the above AEs.

Multiple events will be counted only once per subject in each summary. AEs will be summarized in alphabetic order of SOC and then by PT in descending order of total frequency within each SOC. For summaries by severity, the most severe severity will be used for those AEs that occurred more than once in a subject.

In addition to the above summary tables, TEAEs will be summarized by PT only in descending order of total frequency.

All AE and recorded deaths for the safety population will be listed.

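### ECG abnormality incidence is a primary safety endpoint component in both phases, but SAP 7.4 plans only a listing and does not declare the departure from Protocol 9.4.1

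*SAP*

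**What the plan says.** **Endpoint.** Protocol 3.1 (Table 1) and 3.2 (Table 2) give as a primary safety endpoint "The incidence of AEs, clinical laboratory abnormalities, and ECG abnormalities", for monotherapy and for the combination. SAP 1.2.1 (Table 5) and 1.2.2 (Table 6) repeat it.

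**Protocol analysis.** Section 9.4.1 includes ECGs in its list of safety data: "AEs, clinical laboratory information, vital signs, ECOG performance status, weight, ECGs, and concomitant medications/procedures will be tabulated and summarized".

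**SAP analysis.** Section 7.4 reads in full: "Subjects with abnormal ECG findings will be listed". The SAP's one section on changes from the protocol, 6.3, concerns efficacy only.

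**Adverse-event route.** Protocol 8.3.3, and footnote f of Table 12 in Appendix 1, add: "Any clinically significant changes in ECGs that occur during the study should be reported as an AE in the eCRF". SAP 7.1.6 then says: "The number and percentage of subjects who experienced at least 1 TEAE will be provided and summarized by SOC, PT, and treatment group".

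**Schedule.** Table 12 marks a 12-lead ECG at screening and at 28 (±7) and 100 (±7) days after the last dose. The cells for Cycle 1 Day 1, Cycle 1 Day 8, Cycle 2 and subsequent cycles are empty. Unscheduled ECGs are allowed: "Additional ECGs may be obtained at any time, if clinically indicated".

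**The concern.** An incidence needs a count and the number of patients assessed. A listing of patients with abnormal findings supplies neither as a summary. It leaves out patients whose ECGs were all normal and patients who had no ECG after dosing, so a reader cannot tell these two groups apart or recover the denominator.

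The programming team works from the SAP. If it is followed as written, the study report will have tables for adverse events and laboratory abnormalities but none for ECG abnormalities, although all three stand side by side in the primary endpoint. The report would also depart from Protocol 9.4.1 without a stated reason.

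**Working it through.** The plan states no figure for ECG incidence, so there is none to reproduce. The check sets the sections side by side and then works out the timing.

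**1. Endpoint components against planned output**

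| Component | SAP section | Planned summary |
|---|---|---|
| Adverse events | 7.1.6 | Number and percentage by SOC, PT and treatment group |
| Laboratory abnormalities | 7.2 | Treatment-emergent definition; summary by worst post-baseline grade |
| ECG abnormalities | 7.4 | Listing only; no count, denominator, definition of new or worsened, or window |

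**2. What the TEAE tables cover**

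- *Type of finding.* Only changes judged clinically significant become adverse events. Other abnormal ECGs do not reach SAP 7.1.6.
- *Time.* SAP 7.1.5 ties TEAEs to 28 days after stopping study drug, and footnote s of Table 12 collects adverse events only through the 28-day visit. That visit spans days 28 − 7 = 21 to 28 + 7 = 35 after the last dose, so an ECG in the last 7 days of its window may miss the TEAE cut-off. The 100-day visit spans days 93 to 107, which is 93 − 28 = 65 to 107 − 28 = 79 days past day 28.
- *Denominator.* SAP 7 uses the Safety Analysis Set, which SAP 3.1.1 defines as everyone who received any FPA150, whether or not a post-dose ECG exists.

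**3. When the scheduled ECGs fall**

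Inputs: exposure of median 63 days, range 21 to 233 (Protocol 2.2.5.3, Phase 1a, data cut 31 December 2018); exposure = last dose − first dose + 21 days (SAP 4.2). I assume that this formula underlies the protocol's figures. It fits the median of 3 doses given in the same section, since 3 × 21 = 63.

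First scheduled post-baseline ECG, in days after first dose = (exposure − 21) + 28, ± 7:

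- Median: 63 − 21 + 28 = 70 (63 to 77)
- Shortest: 21 − 21 + 28 = 28 (21 to 35)
- Longest: 233 − 21 + 28 = 240 (233 to 247)

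Protocol 4.6 expects a half-life of about 10 to 20 days. Assuming single-exponential decline, the fraction of the level after the last dose that remains at time t is 2^(−t/half-life):

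- 28-day ECG: 2^(−28/10) = 0.14 to 2^(−28/20) = 0.38
- 100-day ECG: 2^(−100/10) = 0.001 to 2^(−100/20) = 0.03

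The scheduled ECGs therefore support a screening to end-of-treatment comparison. They do not observe patients systematically while they are being dosed.

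**4. What a table would give**

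For a full Phase 1b cohort of 30, all with baseline and post-baseline ECGs, exact (Clopper-Pearson) 95% intervals would be:

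- 0/30: 0% to 1 − 0.025^(1/30) = 11.6%
- 1/30: 0.1% to 17.2%
- 3/30: 2.1% to 26.5%

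The counts are illustrative only. The documents give no observed or assumed ECG abnormality rate.

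**The case against.** The strongest reply is that the ECG findings that matter will be counted. Clinically significant changes must be recorded as adverse events, and those get number and percentage by preferred term. The SAP also looks deliberately short: concomitant medications (5.4) and post-baseline ECOG status (6.2) are likewise only listed. Protocol 9 leaves detailed methods to the SAP and allows deviations to be explained in the study report.

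Much of this stands, and it rules out several stronger readings that a reader might infer:

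- *That the incidence cannot be reported.* It can. Screening and two post-treatment ECGs are scheduled for every patient, and unscheduled ECGs are allowed. The SAP simply does not plan the table.
- *That the component goes wholly unreported.* The TEAE tables cover clinically significant changes within their window.
- *That new abnormalities cannot be told from pre-existing ones.* SAP 3 sorts listings by subject and visit date, and SAP 3.7.3 defines baseline, so a dated listing can show whether a finding was already there at screening.
- *That the enzyme trigger in Protocol 8.3.3 is broken because neither test is in Table 15.* The text is conditional, "Additional ECGs should be obtained at any time if serum creatine kinase (CK) or cardiac troponin is elevated", and footnote b of Table 12 allows tests outside the schedule when clinically indicated. As-needed testing is consistent with that.

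The reply does not remove the gap. The endpoint names ECG abnormalities separately from adverse events, and the adverse-event route omits findings not judged clinically significant and those at the 100-day visit. ECOG status and concomitant medications are not primary endpoint components. The leave to explain deviations in the report softens the missing declaration but supplies no table.

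**Conclusion.** The point holds and should be fixed. One of the three components common to the primary safety endpoint of both phases has no ECG-specific n/N planned in any treatment group, contrary to Protocol 9.4.1 and without explanation. The gap is confined to abnormalities not recorded as TEAEs and to the missing count of patients with a post-dose ECG.

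Its size as a rate is unknown, because the documents give neither an ECG abnormality rate nor the number of patients with post-dose ECGs. Analyses are descriptive (Protocol 9.3) with no formal testing (SAP 3.4), so no decision rule or error rate is affected.

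The absence of ECGs at dosing visits limits what any table can mean. On-treatment ECGs would be event-driven, so a percentage over all treated patients could understate the true rate. That is a limit on interpretation; it does not prevent an end-of-treatment incidence.

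The conclusion rests on the ECG row of Table 12 as it reads in the text. The timing figures in the working also rest on the exposure and half-life assumptions stated there; the main finding does not.

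**What to change.** Add to SAP 7.4 a table by treatment group:

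1. **Numerator:** n (%) of patients with a new or worsened ECG abnormality after first dose, with a statement of what counts as abnormal. The investigator's interpretation under Protocol 8.3.3 is the natural basis.
2. **Denominator:** patients with a baseline ECG and at least one post-baseline ECG, with that number shown.
3. **Window:** stated explicitly, including whether the 100-day ECG counts.
4. **Interpretation note:** because Table 12 schedules ECGs only at screening and after the last dose, the incidence reflects end-of-treatment and unscheduled ECGs and is not a systematic on-treatment rate.

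Keep the listing. If the sponsor decides against the table, the SAP should at least declare and justify the departure from Protocol 9.4.1.

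The endpoint wording and the ECG schedule should be reconciled by the sponsor; no schedule is proposed here.

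Cost: one table and a short definition. Protocol 8.3.3 already has ECG results recorded and interpreted, and SAP 3.7.3 already defines baseline. The tabulation needs no new procedure or data collection.
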